### 3.7 Stopping Criteria

#### 3.7.1 Cohort Stopping Criteria

Formal safety review meetings will be held following each cohort to assess the safety, toleration and pharmacokinetic data collected and decide whether to proceed to the next cohort.

- PK Stopping Criteria: Progression to the next cohort will not proceed if the mean  $AUC_{\tau}$  from existing cohort data exceeds 13550 ng.h/mL.
- Skin Toleration Stopping Criteria: Progression to Cohort 2 will not proceed if 5 or more Cohort 1 subjects, dosed over 40% BSA, have persistent (on at least 3 consecutive occasions) local toleration reactions of  $\geq 5$  total score in the Draize local toleration assessment. Progression to Cohort 3 will not proceed if 5 or more Cohort 2 AD patients, dosed over 40% BSA, report persistent (on at least 3 consecutive occasions) skin related AE's potentially linked to study ointment application as opposed to changes in their normal pattern of AD disease. This includes if a patients' AD worsens beyond tolerability.
- Safety Stopping Criteria: Dose escalation will not proceed if any of the following occur in a ZPL-5212372-treated subject:
  - Severe adverse reaction(s) indicating study drug-related intolerance.

- Clinically significant ECG abnormalities (such as arrhythmias) or effects on other vital signs indicating dose-related intolerance.
- Clinically significant laboratory abnormalities (see Appendix 1 and 2) indicating dose-related intolerance.
- Other findings that, at the joint discretion of the CMO and investigator, indicate dose escalation should be halted.

If any of the above occurs, prompt medical treatment should be provided as appropriate and adverse events promptly reported to the Sponsor via telephone or email.

After satisfactory review of the available pharmacokinetic, safety, and tolerability data progression to the next cohort will occur if the administration to the previous cohort was well tolerated. Adaptive features may be discussed and modifications made based on the safety/PK or learnings from the cohort. Any modifications within the boundaries specified in the protocol will not require a protocol amendment, but will be documented in the minutes of the safety review meeting.

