**Table 1 - Summary of cohorts with overview of study**

	Cohort 1	Cohort 2	Cohort 3
Subject Population	Healthy adults	Moderate to severe AD patients	Moderate to severe AD patients
In-patients/Out-patients	In-patients	In-patients	Out-patients
Total Number of subjects	12	12	30
Ratio Active:Placebo	2:1	2:1	2:1
Dosing Duration	7 days	7 days	14 days
Follow-up Visit (after last dose of study medication)	7-14 days	7-14 days	7-14 days

Progression from Cohort 1 to Cohort 3 will be dependent on the demonstration of adequate safety within the protocol defined boundaries. In Cohorts 1 and 2, complete data sets from a minimum of 4 active and 2 placebo subjects with 40% BSA treated with study ointment will need to be reviewed by the Safety Review Team in order to decide whether to proceed as planned to the next cohort. In the event that it is decided not to proceed to the next cohort, the reviewers may decide to modify the study within the boundaries of the adaptive features and continue, to submit a substantial protocol amendment or suspend the study. In addition,

in order to ensure subject safety, Cohorts 1 and 2 will be split to have an initial sentinel group which will precede the remaining subjects in the cohort. The sentinel group will consist of 3 subjects (2:1 Active to Placebo) and these subjects will be dosed twice daily, to cover 10% BSA with study ointments for 7 days. Provided that the study ointments are well tolerated after 48 hours (i.e. 4 applications) the remainder of the cohort (9 subjects; 2:1 Active to Placebo) may start dosing with coverage of 40% BSA BID for 7 days. All subjects in Cohorts 1 and 2 will remain in the CRU for the duration of the study. Cohort 3 will have AD affected skin dosed to a maximum of 50% BSA. A 50% BSA has been selected as the maximum BSA to be dosed to ensure that the total BSA of AD affected skin is not excessively different from the maximum area of treated skin in Cohorts 1 and 2 (40% BSA). It also accounts for the fact that AD patients total BSA will vary over time due to flare ups of the disease for a multitude of reasons which cannot be controlled within the study, including due to withdrawal from their normal medication prior to randomisation.

[figure not shown]

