**Table 4 - Study Participants**

Adaptive study design category	Adaptive Features	Boundaries
Subject number	
 
1. The number of subjects in Cohorts 1 and 2 may be decreased as there is no formal sample sizing for Cohorts 1 and 2.
 
	
 
1. Upon completion of a cohort the minimum safety data requirements for progression between cohorts is complete datasets for 4 active and 2 placebo subjects treated with 40% BSA coverage of ointments.
 
2. Minimum and maximum evaluable subjects for Cohorts 1 and 2 will be 6 and 12.
 
3. Ratio of 2 active :1 placebo will be used throughout the study.
 

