**Table 5 - Assessments**

Adaptive study design category	Adaptive Features	Boundaries
Assessments	
 
1. Safety/tolerability samples and assessments (such as dermal scoring, safety laboratory, vital signs, ECG's etc).
 
	
 
1. No changes to the timing and frequency of non-safety assessments is allowed.
 
2. Timing and number of safety assessments may change based on clinical need.
 

	
 
2. PK samples: Timing and number of PK samples may change based on the emerging PK profile.
 
	
 
1. There will not be an increase in the number of PK samples taken but fewer samples may be taken.
 
2. Timing of samples may be changed dependent on the emerging plasma concentration data.
 

As the study progresses and safety, toleration and PK data become available the adaptive features of the study may need modifying to improve subject safety and reduce associated risks. Any decisions to modify any adaptive features within the boundaries described in the protocol will be documented and approved (signed) by the CMO prior to any implementation of the modifications. If the protocol requires changes which are outside the boundaries described in the protocol then a protocol amendment will be written. Any associated study documents e.g. informed consent document (ICD), will be updated and re-approved as appropriate.

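### If dosing at 40% BSA in Cohort 1 or 2 is cut to the permitted 4 active and 2 placebo, the fixed skin-toleration trigger of 5 cannot be met by active-arm reactions alone (conditional, minor)

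*Protocol*

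**What the plan says.** Protocol Section 3.7.1 sets the skin criterion for leaving Cohort 1: "Progression to Cohort 2 will not proceed if 5 or more Cohort 1 subjects, dosed over 40% BSA, have persistent" reactions, meaning a Draize total of 5 or more on at least three consecutive occasions. For leaving Cohort 2 it says: "Progression to Cohort 3 will not proceed if 5 or more Cohort 2 AD patients, dosed over 40% BSA, report persistent" skin-related adverse events potentially linked to the ointment. Section 3.6 repeats both criteria and Section 7.5 repeats the Cohort 1 one. None of these restricts the count to active subjects or ties it to the number dosed.

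The plan is for nine subjects per cohort at 40% BSA, allocated 2:1 (Section 3.1). Table 4 in Section 3.2 then allows a smaller cohort: "The number of subjects in Cohorts 1 and 2 may be decreased". The minimum for progression is "complete datasets for 4 active and 2 placebo subjects treated with 40% BSA coverage of ointments", and "Minimum and maximum evaluable subjects for Cohorts 1 and 2 will be 6 and 12". Section 3.1 gives the same minimum: "complete data sets from a minimum of 4 active and 2 placebo subjects with 40% BSA treated with study ointment". The 2:1 ratio applies throughout.

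A reduction must be "documented and approved (signed) by the CMO prior to any implementation of the modifications" (end of Section 3.2). Section 3.7.1 adds: "Any modifications within the boundaries specified in the protocol will not require a protocol amendment".

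**The concern.** The trigger was written as a count for a group of nine, while another part of the protocol lets that group fall to six. Nothing in the protocol or SAP rescales the count. At 4 active and 2 placebo, the pattern the rule most needs to catch, reactions on drug and none on placebo, does not reach it.

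This is the only numeric skin gate between cohorts, in the first topical use of the compound in humans. If it cannot fire on active-arm reactions, the decision to treat diseased skin (Cohort 2), or out-patients over up to 50% BSA (Cohort 3), falls to the remaining gates, which set no number of reactors at 40% BSA.

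**Working it through.** **Inputs.** Cohort of 12 with 3 sentinels at 10% BSA (Section 3.1); 2:1 ratio and the 4+2 minimum (Table 4); trigger of 5 (Sections 3.6, 3.7.1 and 7.5). The documents give no operating characteristic for the trigger and no reaction rates, so the rates in step 3 are assumptions shown as a range.

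**1. The plan's own group sizes.** 12 − 3 = 9 at 40% BSA; 9 × 2/3 = 6 active and 9 × 1/3 = 3 placebo. Six subjects at 2:1 are 4 active and 2 placebo, as Table 4 states. Three sentinels plus six gives nine subjects, inside the 6 to 12 limit, so the reduction is permitted.

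**2. What the trigger requires (no assumptions).** Fewest placebo reactors needed = max(0, 5 − number of actives).

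| Dosed at 40% BSA | Share needed | Placebo reactors needed |
|---|---|---|
| 6 + 3 (planned) | 5/9 = 56% | 0 |
| 5 + 3 | 5/8 = 63% | 0 |
| 5 + 2 | 5/7 = 71% | 0 |
| 4 + 2 | 5/6 = 83% | 1 |

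The criterion counts subjects dosed, not complete datasets. If nine are dosed and only six complete, all six actives still count and the problem does not arise.

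**3. Chance that this one trigger fires.** P(A + B ≥ trigger), with A ~ Bin(actives, pA) and B ~ Bin(placebo, pP) independent. For 4+2, trigger 5 and pA = 1, this is 1 − (1 − pP)²; at pP = 0.1 it is 1 − 0.81 = 0.19. For pA = 0.8 and pP = 0.1 it is 0.8⁴ × 0.19 + 4 × 0.8³ × 0.2 × 0.1² = 0.0778 + 0.0041 = 0.082.

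| pA | pP | 6+3, trigger 5 | 4+2, trigger 5 | 4+2, trigger 4 |
|---|---|---|---|---|
| 100% | 0% | 100% | 0% | 100% |
| 100% | 10% | 100% | 19% | 100% |
| 100% | 20% | 100% | 36% | 100% |
| 100% | 50% | 100% | 75% | 100% |
| 80% | 0% | 66% | 0% | 41% |
| 80% | 10% | 72% | 8% | 49% |
| 80% | 20% | 78% | 16% | 56% |
| 80% | 50% | 91% | 41% | 76% |

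These are probabilities for one criterion, not for stopping overall.

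**4. Overlap with the individual stop.** Section 3.7.2 ends dosing in a healthy volunteer with a persistent grade of 3 or more on any Draize item. The Section 7.5 scales (0–4, 0–4, 0–3) give 5 × 5 × 4 = 100 score combinations. Of these, 66 total 5 or more and 62 of the 66 contain a grade of at least 3. The four that do not (erythema/oedema/desquamation) are 2/2/1, 2/1/2, 1/2/2 and 2/2/2. These are counts of patterns, not probabilities.

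**5. Rescaled counts.** The planned share, rounded up: 6 × 5/9 = 3.3 → 4; 7 × 5/9 = 3.9 → 4; 8 × 5/9 = 4.4 → 5; 9 × 5/9 = 5.

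**The case against.** The strongest reply is that the count of 5 is one gate among several, and that others bite hardest at exactly this size. Most qualifying Draize patterns contain a grade of 3 or more, so if that grade persists the subject's dosing ends under Section 3.7.2. Section 3.8 explains evaluable in terms of completing treatment, and Section 4.8 does not replace subjects who withdraw for adverse events possibly due to treatment. With exactly four actives dosed, losing one could leave the 4-active minimum unmet and so bar progression. Section 3.6 also withholds progression for drug-related intolerance or adverse events. Section 3.7.1 requires that the previous cohort tolerated dosing well, and lists severe reactions and joint discretion of the CMO and investigator as reasons to stop. Four persistent reactors among six would be hard to pass on those terms. Finally, Section 3.6 leaves the running of the review meetings to a separate procedures document, which was not available and may deal with reduced cohorts.

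Much of this stands, and it limits the consequence. It does not close the gap:

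- A persistent 2/2/1 reaction meets the trigger-level score without meeting the individual stop, and need not be severe in the sense of Section 7.16.1.2, which requires that usual activities be prevented.
- In Cohort 2 the individual stop applies only when the investigator judges that the dermatitis has worsened beyond tolerability. Skin events short of that are not covered.
- Section 3.7.2 keeps safety and PK evaluations going after dosing stops, so a dataset could still be called complete.
- The review is of blinded data. SAP Section 11 says some team members may be unblinded, so an all-active pattern could be noticed, but this is not assured.

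A reader might infer that progression would be automatic at 4+2, that the planned nine-subject design is faulty, or that a real progression decision was compromised. The documents support none of these. The other gates apply at every size, and six actives can meet the trigger alone. SAP Section 12 reports very few Draize changes in Cohort 1, SAP Section 3.2 still describes nine subjects at 40% BSA, and neither document reports how many were actually dosed.

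**Conclusion.** The point holds conditionally and is minor. If the number dosed at 40% BSA in Cohort 1 or 2 is cut to 4 active and 2 placebo, the trigger needs 83% of subjects instead of 56%, and at least one of them must be on placebo. That result needs only the protocol's own numbers. If every active subject reacts, the chance that the trigger fires falls from 100% to between 0% and 36% for assumed placebo rates of 0% to 20%. The planned 6+3 group, and any group with five or more actives, is unaffected.

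What is left to judgement at 4+2 is narrow: persistent Draize totals of 5 or more with no grade 3, and Cohort 2 skin events short of intolerable worsening. The conclusion assumes that the unavailable procedures document does not already rescale the trigger.

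**What to change.** In Sections 3.6, 3.7.1 and 7.5, tie the trigger to the number dosed: progression stops if persistent reactions occur in 5 or more subjects when 8 or 9 were dosed over 40% BSA, or in 4 or more when 6 or 7 were dosed, counting every subject dosed over 40% BSA whether or not they completed. Use the same counts for the Cohort 2 skin adverse event criterion in Sections 3.6 and 3.7.1. If the procedures document already does this, a cross-reference is enough. The protocol does not say that 5 was chosen as a proportion, so the safety team may prefer a stricter value. At an 80% active rate and no placebo reactions, a trigger of 4 at 4+2 fires 41% of the time against 66% as planned, so the change narrows the gap without closing it.

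The cost is wording in three sections, with no added subjects or assessments. The downside is more pauses at reduced size when both arms react at the same rate:

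| Common rate | 6 dosed, trigger 5 → 4 | 7 dosed, trigger 5 → 4 | Planned 5 of 9 |
|---|---|---|---|
| 20% | 0.2% → 1.7% | 0.5% → 3.3% | 2.0% |
| 50% | 11% → 34% | 23% → 50% | 50% |

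At these rates the six-subject rule stays below the planned one. The seven-subject rule is slightly above it at 20% and equal to it at 50%. If half of all subjects react, a pause may be wanted anyway.

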### **3.7.2 Individual Stopping Criteria**

- If a healthy volunteer subject has a persistent (on at least 3 consecutive occasions) grade 3 or greater score in erythema, oedema or desquamation, application of study ointment will be discontinued and only safety and PK evaluations will be performed for the remaining scheduled study visits until the AE is resolved.
- If, in the opinion of the investigator, a patient's AD worsens beyond tolerability the patient will have their study medication discontinued and will be followed up until the worsening of their AD has resolved and is under control.

### **3.8 Planned Sample Size and Number of Study Centers**

For Cohorts 1 and 2 it is envisaged that sufficient subjects will be screened to achieve approximately 12 randomised and evaluable subjects (i.e. sufficient subjects completing study treatment to meet the requirements of the data review before proceeding to the next cohort). Recruitment for Cohorts 1 and 2 will be from a single centre in the United Kingdom.

For Cohort 3 it is envisaged that approximately 45 subjects will be screened to achieve approximately 30 randomised and evaluable subjects. Recruitment for Cohort 3 will be from across approximately 4 centers in the United Kingdom. See Section 8.9 for a discussion of sample size.

## **4 STUDY POPULATION**

Upon screening, each subject will receive a 3 digit subject number which will be used throughout the study. Randomisation will occur on Day 1, after all screening procedures have been performed and eligibility for the study confirmed.

Any subjects who terminate their study participation for any reason, regardless of whether study drug was applied or not, will retain their subject number.

Subjects will be randomised on a 2:1 basis to topical 1.0% (w/w) ZPL-5212372 ointment or matching placebo ointment applied twice daily. For the randomisation of subjects, the investigator will use an Integrated Web-based Response System (IWRS). The IWRS will use a computer-generated randomisation schedule to assign subjects to a treatment sequence. For Cohort 3 the randomisation will be stratified based on baseline EASI score (either EASI  $\leq$ 20 or EASI  $>$ 20) to ensure an even distribution of EASI and associated BSA affected across both treatment groups.

To fulfil the study objectives it is essential that appropriate subjects are enrolled. The following eligibility criteria are designed to select subjects for whom protocol treatment is considered appropriate. Subject eligibility should be reviewed and documented by an appropriate member of the site study team. The study population will consist of a cohort of adult healthy volunteers and 2 cohorts of adult patients with moderate to severe AD.

#### **4.1 Inclusion Criteria: Cohort 1**

Healthy volunteer subjects for Cohort 1 must meet all of the following inclusion criteria to be eligible for inclusion in the study

- 1 Healthy males or females, aged between 18 and 55 years, inclusive (healthy is defined as no clinically relevant abnormalities identified by a detailed medical history, full physical examination, including blood pressure and pulse rate measurement, 12-lead ECG and clinical laboratory tests).
- 2 Females should be either of non-child-bearing potential (as specified in Section 4.7) or must agree to use highly effective methods of contraception (as specified in Section 4.7). Males with partners who are WOCBP must also use contraception (as specified in Section 4.7)
- 3 Body weight of  $\geq$  50 kg.
- 4 Body Mass Index of  $\leq$ 34.9 kg/m^2.
- 5 Subjects must have a Fitzpatrick Skin Type of between I to III to be included in the study.
- 6 Willing and able to comply with scheduled visits, treatment plan, laboratory tests and other study procedures.
- 7 Evidence of a personally signed and dated informed consent form, indicating that the subject has been informed of all pertinent aspects of the study.

#### **4.2 Inclusion Criteria: Cohorts 2 and 3**

Moderate to severe AD patients for Cohorts 2 and 3 must meet all of the following inclusion criteria to be eligible for inclusion in the study

- 1 Males and females aged 18-65 years inclusive with physician documented history or diagnosis of atopic dermatitis for at least 6 months prior to screening. AD should be diagnosed by the Eichenfield revised criteria of Hanifin and Rajka.
- 2 Females should be either of non-child-bearing potential (as specified in Section 4.7) or must agree to use highly effective methods of contraception (as specified in Section 4.7).

- Males with partners who are WOCBP must also use contraception (as specified in Section 4.7)
- 3 Body weight of  $\geq 50$  kg.
  - 4 Body Mass Index of  $\leq 34.9$  kg/m^2.
  - 5 Eczema Area and Severity Index (EASI) of  $\geq 9$  and  $\leq 48$  at Screening and an EASI of  $\geq 12$  and  $\leq 48$  at Day 1.
  - 6 An Investigator's Global Assessment (IGA) score  $\geq 3$  at both Screening and Day 1.
  - 7 Atopic dermatitis affecting between  $\geq 10$  to  $\leq 40\%$  BSA at Screening and  $\geq 10\%$  to  $\leq 50\%$  BSA on Day 1.
  - 8 Patients must be willing to stop applying their daily emollients and instead use the study emollient twice daily from at least 7 days prior to randomisation and throughout their participation in the study.
  - 9 Willing and able to comply with scheduled visits, treatment plan, laboratory tests and other study procedures.
  - 10 Evidence of a personally signed and dated informed consent form, indicating that the subject has been informed of all pertinent aspects of the study.

#### **4.3 Exclusion Criteria: Cohort 1**

Healthy volunteer subjects for Cohort 1 presenting with any of the following will not be included in the study:

- 1 Evidence or history of clinically significant haematological, renal, endocrine, pulmonary, gastrointestinal, cardiovascular, hepatic, psychiatric, neurologic, or allergic disease (including drug allergies, but excluding untreated, asymptomatic, seasonal allergies at time of dosing).
- 2 Have tattoos covering areas of skin to be dosed with study ointment.
- 3 Subjects who are hirsute in areas of skin to be dosed with study ointment.
- 4 Subjects who are unwilling to stop hair removal by any means (including shaving, waxing or depilatory creams) to skin areas to be dosed with study ointment for 2 weeks prior to randomisation and throughout the duration of the study.
- 5 Have concomitant skin disease or infection (e.g. acne, impetigo) or presence of skin comorbidities in the study area to be dosed that may interfere with study assessments.
- 6 Hypersensitivity to any excipients in the study ointment formulation, study emollient [REDACTED] or study shower cream [REDACTED]
- 7 Hypersensitivity to any laundry detergents.

- 8 Use of a tanning booth/parlour/sunbathing (including excessive exposure to sunlight) or use of tanning products within 4 weeks before start of the study and for the duration of their participation in the study.
- 9 History of sensitivity to nonsteroidal anti-inflammatory drug(s) (NSAIDs).
- 10 Clinically significant cardiac disease or ECG abnormalities, including:
  - Predominant heart rhythm other than normal sinus rhythm
  - AV block greater than first degree
  - Resting pulse rate >100 or <50 bpm
  - Electrocardiographic evidence or a history of myocardial infarction
  - Electrocardiographic evidence of conduction system abnormality
  - Subjects with pre-randomisation evidence of QTc prolongation (defined as >450 msec).

The PI should decide whether ECG abnormalities other than those listed are clinically significant and should exclude the subject from enrolment.

- 11 Subjects with a personal or family history of prolonged QTc interval.
- 12 Clinically significant liver function tests (LFTs; AST, ALT, total Bilirubin) >1.5 X upper limit of normal (ULN). Subjects with LFTs >1.5 X ULN and <2 X ULN may be retested once.
- 13 Positive HIV, HBsAg and HBcAb result or positive anti-hepatitis C virus serology (as determined by multi-antigen EIA)
- 14 Pregnant and nursing females.
- 15 Donation or intent to donate blood, or blood components during the study or within one month after completion of the study.
- 16 Subjects who have received treatment with an investigational drug within 3 months prior to screening.
- 17 Subjects with a known history (of at least 2 years) of drug abuse.
- 18 A positive urine drug screen.
- 19 Subjects who are smokers (including subjects who use nicotine substitutes).
- 20 History of regular alcohol consumption exceeding 21 drinks/week in males and 14 drinks/week in females (1 drink = 150 mL of wine or 360 mL of beer or 45 mL of spirits) within 6 months of screening.
- 21 Subjects using potent CYP3A4 inhibitors (i.e, cimetidine, clarithromycin, cyclosporine, danazol, dexamethasone, diethyldithiocarbamate, erythromycin, fluconazole, fluoxetine, grapefruit juice, ketoconazole, metronidazole, norfloxacin, omeprazole, ranitidine, sertraline, valproic acid)

- 22 Inability to comprehend or unwilling to follow the study requirements including restrictions on treatments, attendance at out-subject clinic visits and participation in laboratory testing as called for by the protocol.
- 23 Any other severe acute or chronic medical or psychiatric condition or laboratory abnormality that may increase the risk associated with study participation or investigational product administration or may interfere with the interpretation of study results and, in the judgment of the investigator in discussion with the Ziarco CMO, would make the subject inappropriate for entry into this study.

